8.2.8 Medical History (including Smoking History) and Demographic Data

Medical history includes clinically significant diseases, surgeries, cancer history (including prior cancer therapies and procedures), reproductive status, smoking history, use of alcohol and drugs of abuse, and all medications (e.g., prescription drugs, OTC drugs, herbal or homeopathic remedies, THC and its derivative, nutritional supplements) used by the participant within 30 days prior to the screening visit.

Demographic data will include age, sex, and self-reported race/ethnicity and will be recorded in the eCRF.

Smoking history will be assessed by verifying if participant is a current smoker, former smoker, or has never smoked before.

8.2.9 ECOG

Performance status will be measured using the ECOG Performance Status (PS) Scale ([Table 9](#)). It is recommended, where possible, that a participant's performance status will be assessed by the same person throughout the study.

Table 9 ECOG Status

Grade	ECOG Status
0	Fully active, able to carry on all pre-disease performance without restriction
1	Restricted in physically strenuous activity but ambulatory and able to carry out work of a light or sedentary nature, e.g., light house work, office work
2	Ambulatory and capable of all self-care but unable to carry out any work activities. Up and about more than 50% of waking hours
3	Capable of only limited self-care, confined to bed or chair more than 50% of waking hours
4	Completely disabled. Cannot carry on any self-care. Totally confined to bed or chair
5	Dead

Reference: [Oken et al. 1982](#).

8.2.10 Other Non-Safety Assessment(s): Real wOrld PROgnostic score

The ROPRO score must be measured at the time point indicated in the SoA (Section 1.3) and recorded in a “ROPRO calculator” (system to be determined). For the required parameters, see [Table 10](#). Upon entry, the ROPRO value will be reported to the site in order to verify patient eligibility in the study.

Table 10 Real wOrld PROgnostic score

ROPRO Assessments	Parameters
Demographics	Sex, age
Anthropometric measurements	Height, weight
Smoking	Smoking status
Vital signs	Systolic blood pressure, heart rate, oxygen saturation
Hematology	Hemoglobin, platelets, leukocytes, lymphocytes, neutrophils, eosinophils, monocytes
Clinical chemistry	Urea or blood urea nitrogen, calcium, chloride, glucose, total protein, albumin, total bilirubin, ALP, ALT, AST, LDH
Cancer status	Number of metastatic sites*, tumor stage
ECOG performance	ECOG

* Number of metastatic sites does not equal the number of total lesions but the number of organs, which have tumor lesion(s). For example, a participant with two liver lesions and one lung lesion, has two metastatic sites corresponding to two organs that have tumor lesions.

8.2.11 Optional Symptom Questionnaire for Part II Participants

Participants in Part II of this trial will be offered an optional questionnaire to collect symptoms electronically. The questions have been selected on the basis of expected symptoms because of known or potential atezolizumab and RO7296682 adverse drug reactions.

The electronic questionnaire will be self-administered at home at specified time points during the study (see Section 1.3). The questionnaire, translated into the local language as appropriate, will be completed through use of an app downloaded on the participant's own electronic device. The link to download the app and instructions for completing the instruments electronically will be provided by the site staff. If the participant does not have access to a device capable of installing the app, a web link for the electronic completion of the questionnaire may be provided. The data will be transmitted to a centralized database maintained by the electronic device vendor. The data will be available for access by appropriate study personnel.

Participants should be given the following instructions for completing the electronic questionnaire at home:

- Participants should complete the questionnaire in a quiet area with minimal distractions and disruptions.
- Participants should answer questions to the best of their ability; there are no right or wrong answers.

Participants should not obtain advice or help from others to select responses (e.g., family members or friends) when completing the questionnaire.

Adverse event reports will not be derived from this tool by the Sponsor. In addition, the Sponsor will make no attempt to reconcile patient reports of treatment-related symptoms with Investigator reports of AEs. Though the Investigator Sites are not expected to review the data for AEs, they are encouraged to review and to discuss symptoms to keep participant engagement high.

8.3 ADVERSE EVENTS AND SERIOUS ADVERSE EVENTS

The definitions of an AE or SAE can be found in [Appendix 2](#). The NSAESI and disease-related events and/or disease-related outcomes not qualifying as AEs or SAEs are discussed in Sections [8.3.6](#) and [8.3.8](#).

The Investigator and any qualified designees are responsible for ensuring that all AEs (including assessment of seriousness, severity and causality; see [Appendix 2](#)) are recorded on the Adverse Event eCRF and reported to the Sponsor in accordance with instructions provided in this section and in [Appendix 2](#).

Procedures used for recording AEs are provided in [Appendix 3](#).

8.3.1 Time Period and Frequency for Collecting Adverse Event and Serious Adverse Event Information

The method of recording, evaluating, and assessing causality of AEs and SAEs and the procedures for completing and transmitting SAE reports are provided in [Appendix 2](#).

Investigators will seek information on AEs at each participant's contact. All AEs, whether reported by the participant or noted by study personnel, will be recorded in the participant's medical record and on the Adverse Event eCRF as follows:

After informed consent has been obtained **but prior to initiation of study treatment**, only SAEs caused by a protocol-mandated intervention should be reported (e.g., SAEs related to invasive procedures such as biopsies). Any other AE should not be reported.

After initiation of study treatment, all AEs, regardless of relationship to study treatment, will be reported until the safety follow-up visit, or participant discontinuation, whichever occurs first. DLTs will be reported during the DLT assessment window.

Post-study AEs and SAEs: The Investigator is not required to actively monitor participants for AEs after the end of the AE reporting period – that is, after the safety follow-up visit.

However, if the Investigator learns of any SAE (including a death) or other AEs of concern that are believed to be related to prior treatment with study treatment, at any

time after a participant has been discharged from the study, and the Investigator considers the event to be reasonably related to the study treatment or study participation, the Investigator must promptly notify the Sponsor. For the procedure of reporting, see [Appendix 2](#).

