Subsequent Cycles ^b	Day 1	Predose - Atezolizumab and RO7296682	-4h	x	x	x	x	x	x only at cycle of tumor assessment	x only at cycle of tumor assessment	x only at cycle of tumor assessment									
		EOI - RO7296682	+ 30min	x					x only at cycle of tumor assessment											
End of Treatment (EoT) Visit	28 days (± 7) after last dose	At visit		x	x	x	x	x	x	x	x									
Safety FU (135d after last dose)	At visit			x	x	x	x													
In addition, samples to be taken at the following instances:																				
In the event of an IRR/CRS ≥ G2 or with clinical signs of hypersensitivity reaction		At visit		x	x	x	x			x									x	
DLT	At visit			x	x	x	x				x								x	
Unscheduled Visit	At visit			x	x	x	x	x	x	x	x								x	
Any visit																				

Table 3 Pharmacokinetics/Pharmacodynamics for Part II and Part III Dose Expansions

Cycle	Day	Scheduled Time (h)	Time-window	PK RO7296682 ^{a, b, c}	ADA RO7296682 ^{a, b, c}	PK Atezolizumab ^{a, b, c}	ADA Atezolizumab ^{a, b, c}	PD blood FACS	PD Cytokines	Archival sample	Mandatory fresh tumor biopsy ^e	Mandatory healthy skin biopsy ^e	Optional Biopsy ^f	Blood GEP	TCR V β	Clinical Genotyping (DNA)	RBR (DNA)	RBR (RNA)	IgE/Tryptase ^d	ctDNA	WES ctDNA
Pre-screening											x (Part II) ^g										
Screening/ D-28 to D-1											x (Part III)	x	x								
Cycle 1	Day 1	Predose - Atezolizumab and RO7296682	-4h	x	x	x	x	x	x					x	x	x	x	x	x	x	
		EOI - Atezolizumab	+30min			x															
		EOI - RO7296682	+30min	x																	
		EOI - RO7296682	± 2h	x			x		x												
	Day 8	EOI - RO7296682	± 48h	x		x		x	x												
Cycle 2	Day 1	Predose - Atezolizumab and RO7296682	-4h	x	x	x	x	x	x	x											
		EOI - RO7296682	+30min	x																	
	Day 8	168 - RO7296682	± 48h									x	x								
Cycle 3	Day 1	Predose - Atezolizumab and RO7296682	-4h	x	x	x	x							x	x					x	
		EOI - RO7296682	+30min	x																	
Cycle 4	Day 1	Predose - Atezolizumab and RO7296682	-4h	x	x	x	x	x	x	x											
		EOI - Atezolizumab	+30min			x															
		EOI - RO7296682	+30min	x																	
Cycle 5	Day 1	Predose - Atezolizumab and RO7296682	-4h	x	x	x	x													x	
		EOI - RO7296682	+30min	x																	
Subsequent Cycles ^b	Day 1	Predose - Atezolizumab and RO7296682	-4h	x	x	x	x	x	x	x only at cycle of tumor assessment	x only at cycle of tumor assessment										
		EOI - RO7296682	+30min	x																	
End of Treatment (EoT) Visit	28 days (± 7) after last dose	At visit		x	x	x	x	x	x	x	x									x	

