3. OBJECTIVES AND ENDPOINTS

The objectives and corresponding endpoints are provided in [Table 4](#).

Note: Due to the adaptive nature of Part III, additional cohorts, which are not described in this protocol, may be added in the study (see [Appendix 6](#), [Appendix 7](#), [Appendix 8](#), and [Appendix 9](#)). For a rationale, see [Appendix 9](#).

Table 4 Objectives and Endpoints

Objectives	Endpoints
Primary	
All Parts (Dose Escalation [Part I] and Dose Expansion [Part II and Part III])	
To evaluate the safety, tolerability, maximum tolerated dose (MTD) and/or recommended Phase 2 dose (RP2D) (Part I only) of RO7296682 when administered in combination with atezolizumab.	
 • Nature and frequency of adverse events (AEs) with severity determined according to NCI CTCAE v5.0 • Nature and frequency of dose-limiting toxicities (DLTs) in Part I
Primary (Dose Expansion Part II and Part III)	
To evaluate the preliminary anti-tumor activity of RO7296682 when administered in combination with atezolizumab.	
 • Objective response rate (ORR) according to RECIST v1.1
Secondary (Dose Escalation, Part I)	
To evaluate the preliminary anti-tumor activity of RO7296682 when administered in combination with atezolizumab.	
 • ORR according to RECIST v1.1
Secondary (Dose-Escalation [Part I] and Dose Expansion [Part II and Part III])	
To further characterize the anti-tumor activity of RO7296682 when administered in combination with atezolizumab.	
 • Disease control rate (DCR) defined as response rate (RR) and stable disease (SD) • Duration of response (DoR) • Progression-free survival (PFS) 
All according to RECIST v1.1
 
 • Overall survival (OS), if data are mature at the time of analysis
To investigate the pharmacokinetic (PK) profile of RO7296682 and atezolizumab after administration of RO7296682 in combination with atezolizumab.	
 • PK profiles and parameters derived for RO7296682 and atezolizumab, as appropriate, including but not limited to: 
 ○ Area under the curve (AUC) ○ Minimum (C_{\min}) and maximum (C_{\max}) concentration ○ Time of maximum concentration (T_{\max}) ○ Volume of distribution at steady-state (V_{ss}) ○ Half-life ($t_{1/2}$)

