6.5 CONCOMITANT THERAPY

Any medication or vaccine (including over-the-counter [OTC] or prescription medicines, approved dietary and herbal supplements, nutritional supplements) used by a participant within 30 days of study screening until the safety follow-up visit must be recorded on the Concomitant Medications eCRF along with reason for use, dates of administration (including start and end dates) and dosage information (including dose and frequency).

The Medical Monitor should be contacted if there are any questions regarding concomitant or prior therapy.

All medication administered to manage AEs should be recorded on the Adverse Event eCRF.

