6.5.2 Prohibited Therapy

Use of the following therapies is prohibited during the study and for at least 28 days or 5 half-lives of the study drug (whichever is shorter), prior to initiation of study treatment, unless otherwise specified below:

- Investigational or unlicensed/unapproved agents.
- Immunotherapy/radio-immunotherapy.
- Chemotherapy / targeted therapy.
- Radiotherapy (with the exception of limited field palliative radiotherapy).
- Biologic agents (e.g., bevacizumab, cetuximab).
Note: Insulin is allowed.
- Systemic immunostimulatory agents (including, but not limited to, interferons and IL-2) prior to initiation of study treatment and during study treatment because these agents could potentially increase the risk for autoimmune conditions when given in combination with RO7296682 and/or atezolizumab.
- Immunosuppressive medications, including but not limited to cyclophosphamide, azathioprine, methotrexate, and thalidomide. See Section 6.5.1 for guidelines on systemic corticosteroids and TNF- α inhibitors.
- Live, attenuated vaccines (e.g., Flu – Mist® influenza vaccine) are prohibited at any time during the study, and for 5 months following the last dose of study treatment.

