8.11.4 Follow-Up Assessments

Safety Follow-Up/End of Study: Participants who complete the treatment or discontinue from the study early, will be asked to return to the clinic 135 (\pm 30) days after the last dose of study drug or last data point determined for an End of Treatment Visit. Assessments should be completed as detailed in the SoA (Section 1.3).

Survival Follow-Up: The sites will provide to the Sponsor (using a designated section of the eCRF) with an update on survival status 90 (\pm 7) days after the Safety Follow-Up visit and then every 3 months (\pm 2 weeks) thereafter up until 24 months post initial treatment (or until study closure) for each participant enrolled in the study. Patients who screen-failed due to the ROPRO score will also be followed up for survival.

After the study completion/early termination visit, AEs should be followed as outlined in Sections 8.3.1 and 8.3.3.

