9.4.3 Safety Analyses

Unless otherwise specified, all safety analyses listed in [Table 15](#) will be based on the safety population. All safety parameters will be analyzed using descriptive statistics, summarized and presented in tables. Data will be summarized by dose and regimen (if applicable) within each part.

Table 15 Safety Statistical Analysis Methods

Endpoint	Statistical Analysis Methods
Adverse events	
The original terms recorded on the eCRF by the Investigator for AEs will be coded by the Sponsor.
 
Adverse events will be summarized by mapped term and appropriate thesaurus level. The severity of AEs will be graded according to the NCI CTCAE v5.0. Toxicity grade, seriousness, and relationship to study treatment will be presented, as well as summaries of deaths, AEs leading to death and premature withdrawal from study treatment. A glossary of AEs, medication(s), and procedures will be provided.

Clinical laboratory tests	All clinical laboratory data will be stored in the database in the units in which they were reported. Laboratory test values will be presented in International System of Units (SI units; Système International d'Unités) by individual listings with flagging of abnormal results.
Vital signs	Vital signs data will be presented by individual listings with flagging of values outside the normal ranges and flagging of abnormalities. In addition, tabular summaries will be used, as appropriate.
ECG data analysis	ECG data will be presented by individual listings. In addition, tabular summaries will be used, as appropriate.
Concomitant medications	
The original terms recorded on the participant's eCRF by the Investigator for concomitant medications will be standardized by the Sponsor by utilizing a mapped term and appropriate drug dictionary level.
 
Concomitant medications will be presented in summary tables and listings.

Nature and frequency of DLTs	DLT events will be presented by individual listings. The MTD will be estimated with an mCRM-EWOC using DLT evaluable participants. The MTD estimate will be presented along with 90% Credible Intervals.

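### All-cause adverse event frequencies run up to about 135 days past the last dose with no cut or split at a new anti-cancer therapy, so they can include events arising on next-line treatment

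*Combined protocol and SAP*

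**What the plan says.** The primary safety endpoint in all parts (Section 3, Table 4) is "Nature and frequency of adverse events (AEs) with severity determined according to NCI CTCAE v5.0". It is not restricted to related events.

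Section 8.3.1 sets the collection rule: after treatment starts, "all AEs, regardless of relationship to study treatment, will be reported until the safety follow-up visit". The same sentence allows an earlier stop: "or participant discontinuation, whichever occurs first". The schedule of activities and Sections 4.1.1 and 8.11.4 place that visit 135 (±30) days after the last dose. Section 8.11.4 extends it to people who stop early, its figure being in days: "Participants who complete the treatment or discontinue from the study early, will be asked to return to the clinic 135".

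For analysis, Table 15 in Section 9.4.3 says "Adverse events will be summarized by mapped term and appropriate thesaurus level". It adds grade, seriousness, relationship to study treatment, deaths, and events leading to death or to stopping treatment. The safety population in Table 13 fixes which participants count, not which events. Nothing in these sections refers to the start of another anti-cancer therapy.

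Two further places matter. Section 6.5 requires that any medication used "until the safety follow-up visit must be recorded on the Concomitant Medications eCRF", with start and end dates. Section 6.5.2 opens with "Use of the following therapies is prohibited during the study" and lists chemotherapy, targeted therapy and immunotherapy, without saying what applies between the last dose and the safety follow-up visit.

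**The concern.** A participant who stops for progression may begin another systemic treatment well before the safety follow-up visit. Under Section 8.3.1 an event on that treatment is still collected, and under Table 15 it enters the all-cause frequencies reported for RO7296682 plus atezolizumab. The same holds for deaths not attributed solely to cancer progression, which Appendix 3 Section 7 sends to the Adverse Event eCRF whatever their relationship to study treatment.

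The effect is upward, and it grows with the share of the window spent on another drug, so it is larger where progression is faster. Data are summarised by dose within each part, and Section 4.3.3 allows another Part II dose to be explored after a low response rate, with benefit-risk in view. A reader comparing all-cause rates across doses or indications could then mistake faster progression for worse tolerability.

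The efficacy section shows that the plan can limit attribution in time: for duration of response, and for the censoring of progression-free survival, Section 9.4.2 counts deaths only within 30 days of the last study treatment. The primary safety endpoint has no comparable boundary at a new therapy.

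**Working it through.** No alpha, power, sample size or event count in the plan depends on the adverse event window, so there is no stated figure to reproduce. The check has two parts.

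**1. How much of the window follows the last dose**

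Inputs: 21-day cycles (Table 1); first on-study scan at week 8 (Section 8.1.1); safety follow-up at 135 (±30) days (Section 8.11.4). The synopsis and Section 4.4 give ±35 days in the end-of-study definition, a difference that needs reconciling; ±30 is used here.

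- Doses before a week-8 scan fall on Days 1, 22 and 43. If the scan shows progression and dosing stops, the last dose is Day 43.
- Window end: 43 + 135 = Day 178. Share after the last dose: 135/178 = 76%.
- With the visit window: 105/148 = 71% to 165/208 = 79%.

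The share spent on next-line therapy needs a start date, which the documents do not give. The table assumes starts 4, 6 and 8 weeks after the last dose. The second case assumes dosing continues to a week-16 confirmation of progression, which Sections 7.1 and 8.1.1 permit: last dose Day 106, window end 106 + 135 = Day 241.

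| Assumed start after last dose | Days on next-line therapy | Last dose Day 43 | Last dose Day 106 |
|---|---|---|---|
| 28 days | 135 − 28 = 107 | 107/178 = 60% | 107/241 = 44% |
| 42 days | 135 − 42 = 93 | 93/178 = 52% | 93/241 = 39% |
| 56 days | 135 − 56 = 79 | 79/178 = 44% | 79/241 = 33% |

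**2. What this could do to an all-cause rate**

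Let p be the true rate of an event category without next-line therapy, f the fraction of all participants who start such therapy within the window, and q the risk of a new event of that category on it. Taking the two sources as independent, the observed rate is 1 − (1 − p)(1 − f·q). All three inputs are assumed; p = 30%.

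- f = 10%, q = 20%: 1 − 0.70 × 0.98 = 31.4%
- f = 30%, q = 20%: 1 − 0.70 × 0.94 = 34.2%
- f = 60%, q = 40%: 1 − 0.70 × 0.76 = 46.8%

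In a cohort of 20 these are 0.3, 0.8 and 3.4 extra participants with an event (20 × 0.014, 20 × 0.042, 20 × 0.168). The formula ignores death as a competing event, which would lower the upper figures.

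**The case against.** Several points on the other side stand.

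- A reader might infer that next-line toxicity is counted as toxicity of the combination. The documents do not support that. Table 15 presents relationship to study treatment, and Appendix 2 Section 3.2 has causality judged separately for each protocol therapy, with concomitant medications weighed. An event attributed to another drug would appear in the all-cause tables but not as treatment-related. Investigator attribution in an open-label, single-arm study is an imperfect filter, but it is in the plan.
- A reader might also infer that everyone contributes 135 days after the last dose. Section 8.3.1 ends collection earlier at participant discontinuation. Section 7.2 suggests this means leaving the study, yet Section 8.11.4 still calls back those who discontinue from it. If the term meant stopping treatment, the contamination would largely vanish, but late events would be lost.
- There is already an implicit start and end to the window, because before the first dose only SAEs caused by protocol procedures are reported. Only the boundary at a new therapy is missing.
- Next-line uptake may be low. Section 5.1 requires progression on, intolerance to, or unsuitability for standard therapy. Some options may remain: criterion 22 allows no chemotherapy between prior PD-1/PD-L1 treatment and the study in Part II melanoma, and at most one line in the other two tumours.
- The decision consequences are limited. The DLT window closes 7 days after the second dose, cohort opening and futility in Part III use response rate, and no rule acts on a between-dose comparison of all-cause rates.
- Full-window reporting is a defensible conservative choice for a first combination study. A cut alone would shorten observation in fast progressors, could make them look safer, and would rely on relatedness to keep delayed immune-mediated events.

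These points limit the claim and shape the remedy. They do not supply the missing split.

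**Conclusion.** The gap is real and confined to the all-cause tables: overall, Grade ≥3, serious and fatal event frequencies can include events arising on next-line therapy, and the planned output would not show how many. Treatment-related summaries and DLT/MTD estimation are not directly affected.

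The firm figure is 135 of 178 days after the last dose for a participant progressing at the first scan, an early case rather than a typical one. The inflation itself cannot be estimated from the documents. The range from about 31% to about 47% for a true 30% rate illustrates sensitivity to uptake and risk and is not a forecast. Nor can one conclude that a less active dose will look more toxic; that is possible in a descriptive reading, but its direction and size depend on uptake by dose, which is unknown.

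**What to change.** Leave collection under Section 8.3.1 unchanged. In Section 9.4.3 and Table 15:

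1. Present adverse events with onset from first dose to the earlier of the end of adverse event reporting and the day before the first new systemic anti-cancer therapy, plus any later event judged related to study treatment. The date comes from the Concomitant Medications eCRF.
2. Show the full-window all-cause table beside it, so that neither the shorter follow-up nor the reliance on relatedness is hidden.
3. List events with onset on or after the new therapy separately.

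In addition, state in Section 8.3.1 whether participant discontinuation means leaving the study or stopping treatment, and reconcile the prohibition period in Section 6.5.2 with the post-treatment follow-up.

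The cost is one derived date, one extra set of tables and a short wording change, with no new data, visits or participants. The downside is shorter follow-up in the cut table for those who switch therapy early, which is why the full-window table should stay.
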